4.1.2 Subjects Experiencing Significant Elevations Of ALT Due To Acute Exacerbation of CHB

A subject who experiences an extreme elevation of ALT due to acute exacerbation of CHB should be carefully managed at the discretion of the primary investigator. Additional laboratory testing and frequent clinical evaluations are recommended (See [Figure 5.3.2.1](#)).

- An extreme elevation of ALT due to acute exacerbation of CHB is defined as:
 - a serum ALT > 1,000 U/L,OR
 - an elevation in serum ALT > 20x ULN WITH associated clinical or laboratory findings suggestive of hepatic dysfunction,
- Upon investigator request and after discussion and approval by the BMS Central Medical Monitor:
 - A subject who experiences an extreme elevation of ALT due to acute exacerbation of CHB will be provided access to rescue open-label ETV.

The choice of anti-HBV therapy to be used to treat an extreme elevation of ALT due to acute exacerbation of CHB remains at the discretion of the investigator. Only open-label ETV will be provided by the sponsor, and will be limited to those subjects who do not have access to acceptable alternative anti-HBV therapy. Subjects started on rescue open-label ETV will be provided the drug for up to 96 consecutive weeks. Upon completion of the rescue open-label ETV course, subjects will remain on study as part of the LTFU phase until they complete a total of 5 years of study participation from the start of blinded treatment or 48 weeks beyond the completion of rescue open-label ETV; whichever is later. During this time, subjects may be treated with alternative anti-HBV therapy at the discretion of their primary investigator. The sponsor reserves the right to terminate access to rescue open-label ETV if any of the following occur: a) the study is terminated due to safety concerns; b) the subject can obtain medication from a

government sponsored or private health program; or c) therapeutic alternatives become available in the local market.

Specific decisions regarding the management of an extreme elevation of ALT due to acute exacerbation of CHB remain at the discretion of the subject's primary investigator but access to rescue open-label ETV must be discussed with and approved by the BMS Central Medical Monitor.

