## 6 STUDY PERIODS, TREATMENT REGIMENS AND POPULATIONS FOR ANALYSES

### 6.1 Study Periods

Study periods for efficacy and safety analyses are defined as follows:

- **Pre-treatment period** begins at the first visit until initiation of study therapy.
- **On-treatment period** begins after the first day of study therapy and ends at the last dose of study therapy plus 5 days.
- **ETV treatment period** begins after the first day of active ETV and ends at the last dose of active ETV plus 5 days.
- **Off-treatment follow-up period** begins on the last dose of study therapy plus 6 days and ends at the start of alternative anti-HBV therapy minus 1 day.
- **Long-term follow-up period** begins on the last dose of study therapy plus 6 days until the end of the study.
- **Alternative ETV follow-up period** begins on the later of the last dose of study therapy plus 6 days and the start of alternative ETV therapy, until the end of the study.

Note that rescue open-label ETV is considered alternative anti-HBV therapy. See [Section 8.9](#) for additional conventions.

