For PBO-treated subjects who receive open-label ETV, baseline is used during blinded dosing, while ETV baseline is used during open-label ETV dosing.

Laboratory abnormalities by toxicity grade (Grade 1 - 4; Grade 3 - 4) are also summarized by treatment regimen and EOD status (all, normal, abnormal) for the first 2 follow-up cohorts: (1) off-treatment follow-up for off-treatment follow-up subjects in the Post-Year 1 Safety Cohort; (2) long-term follow-up for long-term follow-up subjects in the Post-Year 1 Safety Cohort.

Laboratory abnormalities by toxicity grade (Grade 1 - 4; Grade 3 - 4) are also summarized by treatment regimen during alternative ETV follow-up for alternative ETV follow-up subjects in the Post-Year 1 Safety Cohort.

Emergent laboratory abnormalities by toxicity grade (increased to Grades 1, 2, 3 and 4) are also summarized analogously by treatment regimen and EOD status for the first 2 follow-up cohorts. Emergent abnormalities are those with a higher toxicity grade than the EOD toxicity grade.

Select laboratory elevations and abnormalities are summarized relative to the EOD value for the 3 follow-up cohorts. In addition, elevations of liver function tests (including ALT flares, defined as ALT > 2 x reference and > 10 x ULN) during the follow-up periods are summarized using the reference value (REF) (ie, minimum of the baseline and EOD values) for the 3 follow-up cohorts. Note that for PBO-treated subjects who receive open-label ETV, reference is the minimum of the ETV baseline and EOD values.

ALT multiples of ULN and HBV DNA values are plotted over time for each subject who had an ALT flare on study. The duration of an ALT flare is measured from the first ALT measurement meeting the ALT flare criteria to resolution, defined as (1) the first ALT  $\leq$  baseline or  $\leq 5$  x ULN on treatment, or (2) the first ALT  $\leq$  reference or  $\leq 5$  x ULN during follow-up. If (1) and (2) are not met, an ALT flare is considered unresolved, and the last ALT measurement is used to estimate duration.

The time to and duration of ALT flares (weeks) during off-treatment follow-up are summarized for off-treatment follow-up subjects in the Post-Year 1 Safety Cohort (limited to ETV, PBO OL, and All ETV). Analyses are based on the first ALT flare during off-treatment follow-up.

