### 8.5 Baseline and EOD Measurements

Baseline values are the last non-missing assessments taken prior and up to the first dose of study therapy, or the enrollment date for subject never receiving study therapy, unless specified otherwise.

HBV genotype is derived as the first non-missing assessment regardless of study period. Missing values include those that are labeled “ND” or “UAS”. Indeterminate values are not considered missing.

End of dosing (EOD) values are the last non-missing assessments taken after the first dose of study therapy and up to the last dose of study therapy plus 5 days.

For analyses of ETV treatment for the All ETV Efficacy and Safety Cohorts, the baseline values are the last non-missing assessments taken prior and up to the first dose of active ETV (i.e., “ETV baseline”). For these cohorts, the following parameters are derived only at baseline and

not re-derived at ETV baseline: gender, race, ethnicity, geographic region, country, HBV genotype.

Subjects are excluded from any changes from baseline (or EOD) analysis for which they have a missing baseline (or EOD) value.

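### The SAP defines no reference value at the start of alternative ETV, so an ALT flare or Grade 3-4 abnormality already present then can be counted as an event during it

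*SAP*

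**What the plan says.** SAP Section 7.6.6.1 applies two references in follow-up, and both cover the alternative-ETV cohort.

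- **EOD.** "Select laboratory elevations and abnormalities are summarized relative to the EOD value for the 3 follow-up cohorts". Section 8.5 takes EOD from assessments "taken after the first dose of study therapy and up to the last dose of study therapy plus 5 days", and Section 8.9 leaves rescue ETV out of the dose dates, so starting rescue does not move EOD.
- **REF.** Liver test elevations, and ALT flares (above both twice the reference and 10 x ULN), "are summarized using the reference value (REF) (ie, minimum of the baseline and EOD values) for the 3 follow-up cohorts". For placebo children who went on to open-label ETV, "reference is the minimum of the ETV baseline and EOD values".

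Under SAP Section 6.1 this cohort's period "begins on the later of the last dose of study therapy plus 6 days and the start of alternative ETV therapy", and it runs to the end of the study. Section 8.9 counts both rescue ETV and any concomitant ETV as alternative ETV.

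Protocol Section 4.1.2 defines the extreme elevation that opens access to rescue as "a serum ALT > 1,000 U/L", or ALT above 20 x ULN with findings of hepatic dysfunction.

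Elsewhere the SAP does reset the starting point: for placebo children who switch, "ETV baseline is used during open-label ETV dosing".

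**The concern.** Rescue ETV is given because ALT is already very high. If the comparator is a value from before the flare, an ALT drawn on the start day, or while ALT is falling, can meet the flare definition. The episode being treated then appears as an event on the treatment.

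Three other features of the SAP add to this:

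- The on-treatment and ETV treatment periods begin after the first day of drug, and values up to the first dose serve as baseline (Sections 6.1 and 8.5). The alternative-ETV period can begin on the start day itself, so a start-day value can be an outcome.
- Emergent-grade tables are planned only for the off-treatment and long-term follow-up cohorts. The alternative-ETV cohort gets grade counts with no starting status.
- Section 7.6.6.1 reports each child's highest-grade value in the period, so a single early draw can settle the result.

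Amendment 5 added rescue ETV for safety reasons. The hepatic table for this cohort should let a reader tell a flare under treatment from a new one.

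**Working it through.** The plan states no figure on this point, so there is none to reproduce. The check applies the SAP's rules to ALT values expressed in multiples of ULN.

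**Inputs from the documents**
- Follow-up flare rule: ALT > 2 x reference and > 10 x ULN (SAP 7.6.6.1).
- REF = min(baseline, EOD), or min(ETV baseline, EOD) for placebo children who received open-label ETV.
- Rescue trigger: ALT > 1,000 U/L, or > 20 x ULN with dysfunction (Protocol 4.1.2).
- ALT at entry: 1.5 to < 10 x ULN (Protocol 4.2.1).
- Grade 3 ALT starts at 5.1 x ULN; Grade 4 is > 10 x ULN (Protocol Appendix 2).
- Scheduled LTFU visits: Weeks 6 and 12, then every 12 weeks (Protocol 4.1).

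**Assumptions, not in the documents:** ULN of 30 to 50 U/L, ALT half-life of 1, 2 or 4 weeks, and the ALT courses in the table.

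**Step 1. Does the triggering value meet the REF flare rule?** 1,000/50 = 20 and 1,000/30 = 33, so either trigger is above 20 x ULN under the assumed ULN. If baseline (or ETV baseline) is < 10 x ULN, then REF < 10 x ULN and 2 x REF < 20 x ULN. A trigger above 20 x ULN then exceeds both limits.

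**Step 2. Is it counted in the alternative-ETV period?** Baseline is set at 3 and the value at the start of alternative ETV at 25. The last column uses the start value as the only reference.

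| Course | EOD | REF | ALT in period | Flare by EOD | Flare by REF | Flare by start value |
|---|---|---|---|---|---|---|
| Flare arose in LTFU, start-day draw | 1 | 1 | 25 | yes | yes | no |
| Same, later draw | 1 | 1 | 14 | yes | yes | no |
| Same, first draw already lower | 1 | 1 | 8 | no | no | no |
| Flare on study therapy is the EOD value | 25 | 3 | 18 | no (needs > 50) | yes | no |
| Same, further rise | 25 | 3 | 40 | no (needs > 50) | yes | no (needs > 50) |
| LTFU, new rise | 1 | 1 | 60 | yes | yes | yes |
| LTFU, normalises, later recurrence | 1 | 1 | 22 | yes | yes | no (needs > 50) |

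Rows 1 and 2 are carry-over under both existing references. Row 4 is carry-over through REF only. Row 3 shows that carry-over is not automatic. Row 7 shows what would be lost if the start value replaced the existing references.

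**Step 3. How long does the window stay open?** Halvings needed = log2(start/threshold); weeks = halvings x half-life.

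| Threshold | Start | Halvings | Weeks at half-life 1 / 2 / 4 |
|---|---|---|---|
| Flare (> 10 x ULN) | 20 | 1.0 | 1.0 / 2.0 / 4.0 |
| Flare (> 10 x ULN) | 25 | 1.32 | 1.3 / 2.6 / 5.3 |
| Below Grade 3 (about 5 x ULN) | 20 | 2.0 | 2 / 4 / 8 |
| > 2 x EOD, with EOD 1 x ULN | 20 | 3.3 | 3.3 / 6.6 / 13.3 |

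A start-day or early unscheduled draw would usually be counted as a flare. A first draw at LTFU Week 6 might not be. The Grade 3-4 and > 2 x EOD rows stay open longer than the flare row.

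**The case against.** Several points on the other side are sound.

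- **The EOD mechanism can reverse.** The period starts at the later of last study dose plus 6 days and the ETV start, while EOD runs to last dose plus 5 days. If rescue directly replaces study drug, the start-day ALT falls before the period and can itself be EOD. Against EOD it then counts only if ALT more than doubles again. This stands; carry-over then comes through REF.
- **Early values may not reach the database.** Scheduled LTFU visits are widely spaced, extra visits are discretionary, and Protocol Section 6.3 generally keeps standard-of-care results off the CRF. Against that, Protocol Section 4.1.2 recommends additional testing, Section 5.3.2.1 provides unscheduled kits, and SAP Section 7.1 analyses central or local values. The size is therefore uncertain, but the gap remains.
- **Individual outputs help.** Section 7.6.6.1 plots ALT and HBV DNA over time for each child with a flare and defines flare duration. A reader might infer that a new flare can never be told from the treated one; these plots contradict that. However, no table makes the split, and the time-to-flare and duration summaries cover off-treatment follow-up only.
- **Not every child is affected.** Concomitant ETV can start without a flare. ALT > 1,000 U/L qualifies for rescue without liver dysfunction, so abnormal bilirubin or INR at the start is not implied.
- **Resetting the reference could do harm.** The period runs to the end of the study. If only values above the start value counted, a recurrence at 22 x ULN after a start at 25 would disappear. This is a good reason to add the start value and keep the existing references.

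**Conclusion.** The gap is real but conditional. Every reference for the alternative-ETV cohort predates that ETV, the start day can fall inside the period, and no rule separates an abnormality already present from a new one. The indication for rescue can therefore be tabulated as an event during rescue, provided a value in the period still meets the criteria.

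A reader might infer that the triggering flare is always counted, or that the flare rate in rescued children would approach 100%. The documents support neither. The second is an upper bound that needs an early qualifying ALT from every child, and the number of rescued children and the timing of their draws are not given. ALT at the first dose may also differ from the trigger value, because approval precedes dosing.

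Only descriptive safety tables are affected; no hypothesis test or efficacy endpoint depends on them. Step 1 assumes the stated ULN range and a baseline (or ETV baseline) below 10 x ULN. The week counts rest on the assumed half-lives.

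**What to change.** In SAP Section 7.6.6.1, for the alternative-ETV cohort:

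1. Keep EOD and REF. Add an alternative-ETV baseline: the last non-missing value up to the first dose of alternative ETV.
2. Report ALT, bilirubin and INR at that baseline.
3. Tabulate abnormalities and flares ongoing at the start separately from new ones. Call a flare new if it meets the REF criteria and (a) follows resolution by the SAP's own rule (ALT at or below reference, or <= 5 x ULN), or (b) arises in a child with no flare at the start, or (c) is a further rise above the starting value.
4. Add an emergent-grade table against the alternative-ETV baseline.

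Do not require every new flare to exceed the starting value, because that would hide later recurrences.

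The cost is SAP wording, one more derived value and a few more table rows. No new data collection is needed.

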4.1.1 Subject Management Decisions

Assessment of HBeAg seroconversion will be done, as needed, at Study Weeks:

- 52 (based upon Week 48 result);
- 100 (based upon Week 96 result); and
- 148 (based upon Week 144 result).

The investigators shall conduct the assessment of HBeAg response status at the assessment time points; this will be cross checked centrally by the BMS Medical Monitor/Protocol Manager. Subjects achieving HBeAg seroconversion shall initiate consolidation therapy for an additional 48 weeks as follows:

- At Week 52 (consolidation using blinded therapy to Week 96; 48 weeks counting from Week 48)
- At Week 100 (consolidation using open-label ETV to Week 144; 48 weeks counting from Week 96)
- At Week 148 (consolidation using open-label ETV to Week 192; 48 weeks counting from Week 144)

Subjects who achieve HBeAg seroconversion and revert back to HBeAg-positivity or develop HBeAg-negative CHB shall be managed as follows:

- Any subject who achieves HBeAg seroconversion by the Week 48 assessment and reverts to HBeAg-positive status before reaching Week 96 will be treated with open-label ETV until study Week 144, and then will stop study therapy and proceed to the LTFU phase;
- Any subject who achieves HBeAg seroconversion after the Week 48 assessment, who reverts back to HBeAg-positive status shall stop study treatment, if applicable, and be treated at the discretion of the investigator in consultation with the BMS Medical Monitor.
- Subjects who develop HBeAg-negative CHB (absence of HBeAg, presence of anti-HBe antibodies, active viral replication [HBV DNA by PCR assay $\geq 10,000$ copies/mL] and biochemical or histological evidence of hepatitis) shall be managed at the discretion of the investigator in consultation with the BMS Medical Monitor.

Study treatment (ETV and placebo) shall be provided during the blinded and open-label study treatment phases. Rescue open-label ETV shall be provided to subjects who experience extreme elevations of ALT due to acute exacerbations of CHB upon investigator request and approval by the Central Medical Monitor (see section 4.1.2).

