## 2 STUDY DESCRIPTION

### 2.1 Study Design

This is a comparative, randomized, double-blinded, placebo-control, multicenter study, assessing the efficacy and safety of ETV in pediatric subjects with chronic HBV infection who are HBeAg-positive and nucleos[t]ide naive (< 12 weeks of prior therapy with any nucleos[t]ide antiviral agent with activity against hepatitis B virus). Chronic HBV-infected children and adolescents from 2 to < 18 years of age will be enrolled. Approximately 180 subjects will be randomized 2:1 to ETV or placebo (PBO) for a maximum of 96 weeks of blinded therapy, with the primary endpoint at Week 48 for the first 123 randomized subjects (the Primary Cohort). The randomization will be stratified by age group ( $\geq 2$  to  $\leq 6$ ,  $> 6$  to  $\leq 12$ ,  $> 12$  to  $< 18$  years). To ensure adequate representation, the target enrollment will be 30 subjects for each age group, with a minimum requirement of 18 subjects. At Week 52, an assessment of HBeAg seroconversion shall be performed based on Week 48 serology results. At the Week 52 assessment, all subjects who achieve HBeAg seroconversion will remain on blinded therapy through Week 96; subjects without HBeAg seroconversion will be switched to open-label ETV. Thereafter, assessment of HBeAg seroconversion shall be conducted at study Weeks 100 and 148 during the open label treatment. Study subjects who achieve HBeAg seroconversion during open label ETV at the respective assessment time points shall receive up to an additional 48 weeks of study treatment for consolidation (extended treatment to strengthen study drug effects). Open-label ETV may therefore be continued up to Week 144 in ETV randomized subjects and Week 192 for placebo randomized subjects. All randomized study subjects who do not achieve HBeAg seroconversion will receive a maximum of 96 weeks of study ETV therapy.

After completing the blinded treatment or the open-label phase, all subjects will be followed in an observational long-term follow up phase until they complete a total of 5 years of study participation from the start of blinded treatment.

The total duration of the study will be 264 weeks (5 years); the end of the study is defined as the date of the last follow-up visit. Study visits will occur at screening, Baseline, Weeks 4, 8, 12, and

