### **7.6.2 Other Serious Adverse Events**

Pre-treatment SAEs are summarized by treatment regimen for enrolled subjects (ETV, PBO, not treated). Pre-treatment SAEs are those that occurred prior to the first dose of study therapy.

SAEs are also summarized by treatment regimen for the following cohorts and study periods:

- Through Week 48 on blinded therapy for treated subjects
- After Week 48 on blinded therapy or on open-label ETV through Week 96 for the Year 2 Safety Cohort
- On ETV treatment for the All ETV Safety Cohort
- Off-treatment follow-up for off-treatment follow-up subjects in the Post-Year 1 Safety Cohort
- Long-term follow-up for long-term follow-up subjects in the Post-Year 1 Safety Cohort
- Alternative ETV follow-up for alternative ETV follow-up subjects in the Post-Year 1 Safety Cohort.

SAEs leading to death and SAEs related to study therapy and leading to death are also summarized analogously during the on-treatment period for the 3 cohorts.

Multiple on-treatment SAEs (all; related to study therapy) are also summarized for the 3 cohorts, presenting the numbers of events and exposure-adjusted incidence rates (see [Section 8.10](#)).

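### Off-treatment ALT flares and SAEs are shown as whole-period percentages over unequal follow-up (about 120-168 weeks for ETV, 72-120 for PBO OL), with no person-time rate or censored incidence

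*SAP*

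**What the plan says.** **When study drug stops.** SAP 2.1 plans 264 weeks of participation. For Week 48 responders, "all subjects who achieve HBeAg seroconversion will remain on blinded therapy through Week 96". For the rest, "All randomized study subjects who do not achieve HBeAg seroconversion will receive a maximum of 96 weeks of study ETV therapy", with a consolidation extension for those who seroconvert on open-label drug: "Open-label ETV may therefore be continued up to Week 144 in ETV randomized subjects and Week 192 for placebo randomized subjects". Protocol 4.1.1 describes the longest course as "consolidation using open-label ETV to Week 192; 48 weeks counting from Week 144".

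**What counts as off-treatment follow-up.** Under SAP 6.1 the period starts 6 days after the last dose of study therapy and closes the day before any alternative anti-HBV therapy. Rescue ETV counts as alternative therapy.

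**How events are summarized.** SAEs are tabulated by regimen for "Off-treatment follow-up for off-treatment follow-up subjects in the Post-Year 1 Safety Cohort" (SAP 7.6.2). That cohort has columns for ETV, PBO, PBO BL, PBO OL and All ETV (SAP 6.3). SAP 7.6.6.1 adds a summary of "elevations of liver function tests (including ALT flares, defined as ALT > 2 x reference and > 10 x ULN) during the follow-up periods". The default for categorical data is counts and percents (SAP 7.1). One laboratory measurement in the period puts a child in the laboratory denominator (SAP 7.6.6).

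**Time-related outputs.** Exposure-adjusted incidence rates are specified for on-treatment events, with time on study therapy as the denominator (SAP 7.6.2, 7.6.5, 8.10). Time to first off-treatment flare and its duration are summarized for ETV, PBO OL and All ETV: "Analyses are based on the first ALT flare during off-treatment follow-up". No censoring rule is given. Time in off-treatment follow-up is reported by regimen (SAP 7.4.1).

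**The concern.** A whole-period percentage depends on the event rate and on how long each child was watched. Here the second factor differs by design between columns printed next to each other. All else equal, a column with longer observation shows more flares, and a column in which children restart therapy sooner shows fewer, because restarting closes the period.

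This matters because the documents treat exacerbation after stopping as a principal risk. Protocol 1.5 notes that exacerbations have been observed in post-treatment follow-up, and Protocol 5.3.2.1 describes their potential severity. Off-treatment and long-term safety is also the stated minimum content of the final analysis (SAP 9). A reader of those tables will want the risk of a flare by a given time after stopping, and no specified output gives it.

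**Working it through.** **1. Reproduce the plan's stop times.** Consolidation adds 48 weeks: 96 + 48 = 144 and 144 + 48 = 192. Both agree with SAP 2.1.

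**2. Planned off-treatment follow-up = 264 - stop week.**

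| Column | Path | Stop (week) | Follow-up (weeks) |
|---|---|---|---|
| ETV | Week 48 seroconverter, or non-seroconverter at Weeks 48 and 96 | 96 | 168 |
| ETV | Week 96 seroconverter, or Week 48 seroconverter who reverts | 144 | 120 |
| PBO OL | Week 96 seroconverter, or non-seroconverter throughout | 144 | 120 |
| PBO OL | Non-seroconverter, 96 weeks of ETV counted from Week 52 | 148 | 116 |
| PBO OL | Week 144 seroconverter | 192 | 72 |
| PBO BL | Week 48 seroconverter | 96 | 168 |

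Chemistry is drawn at follow-up Weeks 6, 12 and every 12 weeks (Protocol Table 6.1). So 168, 120 and 72 weeks give 15, 11 and 7 scheduled chances to detect a flare.

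**3. Mean follow-up by column.** The documents do not give the share on the extended course, so 0-30% is assumed.
- 0%: 168 / 120 = 1.40.
- 10%: (0.9 × 168 + 0.1 × 120) / (0.9 × 120 + 0.1 × 72) = 163.2 / 115.2 = 1.42.
- 30%: 153.6 / 105.6 = 1.45.

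**4. Effect on crude percentages when true rates are equal.** The documents give no event or restart rates, so these are assumptions too. With event rate λ and alternative-therapy rate α per year, and t years of follow-up, the expected crude percentage is λ/(λ+α) × [1 - exp(-(λ+α)t)]. With 10% on the extended course in each column:

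| λ per 100 PY | α per 100 PY | ETV | PBO OL | Ratio |
|---|---|---|---|---|
| 5 | 0 | 14.5% | 10.4% | 1.39 |
| 10 | 0 | 26.8% | 19.8% | 1.36 |
| 20 | 0 | 46.4% | 35.6% | 1.30 |
| 5 | 50 | 7.4% | 6.4% | 1.17 |
| 10 | 50 | 14.1% | 12.2% | 1.16 |
| 20 | 50 | 25.3% | 22.3% | 1.13 |

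If all events occur within 72 weeks of stopping, every planned path covers the risk period, and planned length alone produces no difference at the final analysis.

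**5. Earlier data cuts.** SAP 9 also runs safety analyses before the final one. Take a child 168 weeks from first dose. Stopping at Week 96 gives 168 - 96 = 72 weeks off treatment. Stopping at Week 144 or 148 gives 24 or 20. The ratio is 3.0 to 3.6, so early clustering of events gives less protection at these cuts.

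**6. Same rates, fixed horizon.** Cumulative incidence at Week 72 with α = 0 is 6.7%, 12.9% and 24.1% for λ = 5, 10 and 20, identical in both columns.

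**The case against.** **These tables are descriptive.** This stands. Differences with p-values are reserved for the primary and key secondary efficacy endpoints. The only formal off-treatment comparison (SAP 7.5.2.5) is at a fixed time, Week 24. ETV and PBO OL are both ETV-exposed groups, not a randomized contrast. A reader might infer that a planned conclusion is biased, but none is.

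**Other outputs help.** This stands in part. Time in follow-up is reported by regimen, so unequal observation will be visible. ALT categories and values by visit (SAP 7.5.8, 7.6.6.2) align follow-up time, and individual profiles are plotted for each child who flared. Parallel long-term follow-up summaries continue past the start of alternative therapy. Calling the columns simply non-comparable would therefore go too far. But the by-visit categories stop at > 5 x ULN, while a flare needs > 10 x ULN and > 2 x reference, and follow-up time is never used as a denominator. None of these outputs gives flare incidence.

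**Time to flare may already be handled properly.** It is tempting to say that it covers only children who flared. The SAP does not say so: it names off-treatment follow-up subjects, and table formats are left to a separate Data Presentation Plan. The supportable criticism is that no censoring rule or estimator is stated, although SAP 7.4.1 does specify Kaplan-Meier for time on therapy.

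**Non-serious AEs.** A reader might extend the point to all AEs. That is weak. Footnote e of Protocol Table 6.1 records AEs at follow-up Week 6 for children not on rescue ETV, and every planned path reaches Week 6. Protocol 6.3.2 and 7.3.3 state no time limit for drug-related or discontinuation-related AEs, so these passages should be reconciled. SAEs are to be reported during long-term follow-up (Protocol 7.3.1).

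**Week 264 is not a universal end.** Correct: children given rescue ETV may stay longer (Protocol 4.1). Rescue closes off-treatment follow-up under SAP 6.1, so the extension lengthens long-term follow-up and leaves the windows above unchanged.

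**Conclusion.** The point holds for off-treatment ALT flares and SAEs. The ETV column has about 1.4 times the planned observation time of PBO OL, All ETV pools the two, and the SAP specifies neither a person-time rate nor a censored incidence for follow-up. The columns and the pooled figure are not directly comparable.

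The follow-up lengths come from the documents; the size of the distortion does not. The 7-point gap in the table (26.8% against 19.8%) is one illustration, resting on a constant 10 per 100 person-years, no restarts and 10% on the extended course. Over the assumptions shown, the ratio runs from 1.39 down to 1.13, and to no difference at the final analysis if every event falls within 72 weeks. Imbalance in observation time is relatively larger at the earlier cuts. This is a worthwhile improvement to descriptive safety reporting. It does not threaten the efficacy conclusions.

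**What to change.** In SAP 7.6.2 and 7.6.6.1, for first off-treatment ALT flare and first off-treatment SAE, add by regimen:

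- First events per 100 person-years of off-treatment follow-up. Person-time runs to the first event, otherwise it is the off-treatment time defined in SAP 7.4.1. SAP 8.10 needs a matching follow-up denominator, since it now defines exposure only as time on study therapy.
- Cumulative incidence at off-treatment Weeks 24, 48 and 72, with numbers at risk. Week 72 is the shortest planned follow-up. Start of alternative anti-HBV therapy is a competing event; end of follow-up or data cut-off is censoring.

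Keep the existing time-to-flare and duration summary, labelled as a description of subjects who flared. Apply the additions at every data cut in SAP 9 that reports follow-up safety.

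The cost is one extra table and plot from dates the SAP already derives (7.4.1, 8.9), with no change to data collection or patient management. The drawback is small numbers at risk at the later weeks, especially in PBO OL at the earlier cuts.
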